2.2 Randomization Methodology

A total of 80 subjects are to be randomly assigned in a 1:1 ratio to one of two arms using permuted block randomization: (1) placebo or (2) famotidine. Subject randomization will be stratified by NYHA/WHO Functional Class (NYHA/WHO Functional Class II versus Class III/IV) to ensure balanced representation of this important marker of severity. A randomization code will be computer-generated by contract research organization (CRO) Axio Research, LLC. Subjects meeting study entry criteria will be randomized via an interactive web response system (IWRS). The randomization schedule will be generated by the randomization statistician at Axio Research (who is not on the project team) or designee and maintained in a secure and limited-access location separate from the study investigator and members of the project team. The study subject, investigative staff, the Sponsor, the Sponsor study team (includes contractors and vendors), excluding the unblinded study site pharmacist will be blinded to treatment assignments during the study.

2.3 Stopping Rules

Not applicable, see Section 2.5.

2.4 Blinding

This is a double-blind study in which all participants, Investigators, and study personnel involved in the conduct of the study, including data management, are blinded to treatment assignment except for:

- An unblinded independent statistician or designee who will prepare and have access to the randomization code
- The unblinded pharmacist at study site

Although unblinded to treatment assignment, none of the above roles will have access to unblinded summaries of efficacy or safety data.

The following personnel will have access to unblinded efficacy and safety data in order to discharge their roles for data analysis and periodic safety review meetings:

- The unblinded statistical programming team and independent DSMB support statistician who will prepare the unblinded reports for review

Other than the above-mentioned personnel, all other individuals involved in the study conduct, statistical analysis and reporting will remain blinded until the after official study unblinding at the end of the study. The DSMB will review masked data by treatment arm with the option to unmask during the meeting. One DSMB member asking for unmasking is sufficient for unmasking of the DSMB to occur. The DSMB also has the option to unmask only for a single individual safety event (e.g., a death).

2.5 Interim Analyses

Reports to the Data and Safety Monitoring Board (DSMB) will focus on trial integrity (recruitment, protocol deviations/violations, completeness of follow-up and adherence) and safety. Comprehensive safety interim reports will be provided semi-annually to the DSMB. Comprehensive, safety reports will include detailed summaries of all SAEs, AEs, laboratory parameter listings, drug discontinuations and withdrawals as well as other pertinent safety data. The DSMB will recommend continuation or discontinuation of the study based on these interim reviews. Because of the length, size, and scope of the proposed study interim analyses for efficacy or futility will not be performed.

3 STUDY ENDPOINTS

3.1 Efficacy Variables

The study objectives and efficacy endpoints are summarized in Table 3-1.

Table 3-1: Study objectives and endpoints

OBJECTIVES	ENDPOINTS	JUSTIFICATION FOR ENDPOINTS
Primary		
To determine whether famotidine increases six-minute walk distance at 24 weeks in men and women with pulmonary arterial hypertension.	The primary endpoint is the change in six-minute walk distance (6MWD) between baseline and 24 weeks. This will be compared between treatment groups.	The six-minute walk distance is simple, reproducible, and well tolerated in patients with PAH. The 6MWD has been the primary outcome measure for the majority of pivotal trials of PAH therapeutics because of its relationship to hemodynamic parameters, treatment outcome, and survival.
Secondary		

To determine whether famotidine reduces BNP at 24 weeks
 
To determine whether famotidine improves New York Heart Association (NYHA) functional class at 24 weeks
 
To determine whether famotidine improves right ventricular morphology at 24 weeks including improved right ventricular dilation and TAPSE
 
To determine whether famotidine improves health related quality of
	Secondary endpoints include the change in BNP, NYHA functional class, right ventricular basal diameter, TAPSE, emPHasis-10 score, and the frequency with which routine therapies for patients with PAH are escalated during the trial.	Secondary outcomes were chosen to better understand the impact of the intervention on various aspects of the treatment response including health-related quality of life using disease specific validated tools.

life as estimated by the emPHasis-10 score
 
To determine whether famotidine decreases the need to escalate PAH focused care (increased diuretics, escalating doses of pulmonary vasodilators, and/or adding an additional pulmonary vasodilator)
		

Tertiary/Exploratory
		

Exercise sub-study:
 
To determine whether famotidine increases maximal oxygen uptake in individuals with pulmonary arterial hypertension at 24 weeks
 
To explore changes in other metrics of the exercise response (oxygen uptake, V_e/V_{CO_2} ratio, total achieved wattage) with famotidine relative to placebo over 24 weeks.
 
Right heart catheterization sub-study:
 
To determine whether famotidine increases stroke volume index at 24 weeks
 
To explore whether famotidine is associated with differences in wedge pressure, right atrial pressure, and/or pulmonary vascular resistance at 24 weeks
	
The primary analyses will be the change in oxygen consumption (VO_2) for the exercise sub-study and the change in stroke volume index (SVi) for the right heart catheterization sub-study conducted using the FAS.
 
Qualitative descriptions of other exercise and hemodynamic markers including mean, median, and distribution will be presented stratified by treatment group.
	
While the two proposed sub-studies are powered to detect plausible, but large differences in exercise response or invasive hemodynamic markers, these studies are not powered to detect small to moderate differences. The co-primary intent of these sub-studies is to begin to understand appropriate end-points in trials of right heart targeted therapy. This more exploratory motivation is intended to complement but not supplant primary and secondary outcome measures.

3.2 Pharmacokinetic Variables

Not applicable.

3.3 Safety Variables

Safety assessments performed during the study included physical examinations, measurement of vital signs (includes height, blood pressure, heart rate, oxygen saturation), weight, symptom assessment, clinical laboratory evaluations including comprehensive metabolic panel, complete blood count, pregnancy test (if premenopausal), and monitoring of adverse events.

4 ANALYSIS SETS

4.1 Analysis Set Definitions

The following Analysis sets will be evaluated and used for presentation and analysis of the data:

- **Screening Analysis Set:** Includes all subjects who signed the informed consent form.
- **Enrolled Analysis Set:** Includes all subjects in the Screening Analysis Set who were assigned a randomized treatment.
- **Full Analysis Set (FAS):** Includes all randomized subjects who received at least 1 dose of study medication. Subjects will be analyzed according to their randomized treatment.
- **Per Protocol (PP) Set 1 (PPS1):** Includes all subjects in the FAS whose famotidine medication reconciliation suggest adherence to study drug for 80% or more of administered doses. Subjects will be analyzed according to their randomized treatment.
- **Per Protocol (PP) Set 2 (PPS2):** Includes all subjects in the FAS who (1) were randomized to famotidine for whom H₂ receptor antagonists are detected by mass spectrometry at the final visit and (2) those randomized to placebo for whom H₂ receptor antagonists are not detected at the final visit. Subjects will be analyzed according to their randomized treatment.
- **Safety Analysis Set (SAF):** Includes all randomized subjects who received at least 1 dose of study medication. Subjects will be analyzed according to their actual treatment. Actual treatment is defined as the treatment received for most of the days during the treatment phase of the study.

Per ICH-E9 [1] and ICH-E9-R1 [2] guidelines, will use FAS instead of intention-to-treat. The FAS will be the primary analysis set for the analysis of the primary and secondary efficacy endpoints.

The PPS1 and PPS2 will be used in the sensitivity analyses of the primary and secondary efficacy endpoints.

The SAF will be the primary set for the analysis of the safety parameters.

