9.3 POPULATIONS FOR ANALYSES

Intent-to-Treat Population: All subjects who are randomized will comprise the intent-to-treat (ITT) population. The ITT population will be analyzed for the primary and secondary endpoint analyses and will comprise the safety population used for all safety analyses.

Per Protocol Population: Subjects in the ITT population whose famotidine medication reconciliation suggest adherence to study drug for 80% or more of administered doses will be evaluated as the per protocol population. The per-protocol population will be used in the sensitivity analyses of the primary and secondary endpoints. A second per protocol population will include participants for whom H₂ receptor antagonists are detected by Mass Spectrometry at the final visit relative to those for whom H₂ receptor antagonists are not detected.

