5.4 Withdrawals, Dropouts, Loss to Follow-up

Discontinued subjects will not be replaced whether they received or did not receive the study drug. The multiple imputation approach is included in Section 6.4.

Follow-up of subjects who discontinued the study drug early will continue until Week 24 and the study procedures will be assessed as per the schedule of assessment (see Table 9-1).

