6.4.1.1 Sensitivity analysis

Sensitivity analyses will be performed using the PPS1 and PPS2 analysis sets instead of FAS.

Although every effort will be made to avoid missing data, a range of approaches to missing 6MWD will be considered as sensitivity analyses representing a range of conservative and anti-conservative biases to describe the range of possible differences.

Sensitivity analyses of the primary endpoint will include:

- 1) • a linear regression model using a worst case scenario (WCS) method of imputation
- 2) • a linear regression model of the 24 week 6MWD without imputation (complete case analysis)

(1) The worst case scenario method of imputation will impute zero for all missing 6MWD at week 24.

(2) The linear regression method will model the 24 week 6MWD on treatment assignment, adjusting for baseline 6MWD and baseline NYHA functional class using least squares and robust standard error estimates.

For all methods, treatment effect estimates and 95% CIs will be presented.

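### PPS2 requires evidence of drug intake in the famotidine arm but none in the placebo arm, so this sensitivity analysis is biased toward famotidine if participants who stop tablets do worse regardless of drug

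*SAP*

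**What the plan says.** SAP 4.1 builds PPS2 from the FAS, that is, from everyone randomised who took at least one dose. Its two entry conditions differ by arm:

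- Famotidine: those who "were randomized to famotidine for whom H₂ receptor antagonists are detected by mass spectrometry at the final visit".
- Placebo: "those randomized to placebo for whom H₂ receptor antagonists are not detected at the final visit".

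The tablet-count rule, "adherence to study drug for 80% or more of administered doses", belongs to PPS1 only. PPS2 is not nested in PPS1, so it does not inherit that rule.

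On use, SAP 4.1 states: "The PPS1 and PPS2 will be used in the sensitivity analyses of the primary and secondary efficacy endpoints". SAP 6.4.1.1 repeats this for the primary endpoint ("Sensitivity analyses will be performed using the PPS1 and PPS2 analysis sets instead of FAS"), and SAP 6.4.2 for the secondary endpoints. The FAS is the main set throughout.

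SAP 5.4 keeps people who stop tablets under observation: "Follow-up of subjects who discontinued the study drug early will continue until Week 24".

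Protocol 9.3 describes the set differently: "A second per protocol population will include participants for whom H₂ receptor antagonists are detected by Mass Spectrometry at the final visit", compared with those in whom none is detected. It does not mention the randomised arm. SAP 7 lists changes from the protocol, and this is not among them.

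**The concern.** The assay answers a different question in each arm. On famotidine, a positive result is evidence of recent intake. On placebo, which contains no active drug (Protocol 6.1.1), a negative result shows only that no outside H2 antagonist was detected. It says nothing about whether placebo was taken. The same behaviour, stopping tablets while remaining in follow-up, leads to exclusion in one arm and inclusion in the other.

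If those who stop have worse outcomes irrespective of drug, PPS2 compares a selected famotidine group with a less selected placebo group. A PPS2 estimate larger than the FAS estimate would then look like a benefit of confirmed exposure when selection alone could have produced it. This applies to the primary endpoint and to every secondary endpoint.

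**Working it through.** **Inputs from the documents.** 80 participants randomised 1:1, so 40 per arm (SAP 2.2); SD 37.6 m and design effect 31.9 m (SAP 6.1); two-sided 0.05 (SAP 6.2.1).

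**The plan's own figure.** With 40 per arm the standard error is 37.6 × √(2/40) = 8.41 m and the noncentrality is 31.9/8.41 = 3.79. The two-sample t-test has power 0.963 (stated 0.96), and 0.944 at 36 per arm (stated 0.94). The design inputs reproduce. The documents give no figure for PPS2.

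**Bias under no drug effect.** Let f be the share of each arm not taking tablets at Week 24, D their deficit in metres relative to takers in either arm, and μ the takers' mean change.

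- Famotidine arm in PPS2 (takers only): mean μ.
- Placebo arm in PPS2 (takers and non-takers): mean μ − f × D.
- Difference: f × D in favour of famotidine.

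Both f and D are assumptions. Simulated results (40,000 trials per row, 40 per arm, SD 37.6, no drug effect, unadjusted t-test):

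| f | D (m) | f × D (m) | % of 31.9 m | PPS2 rejects | Non-takers removed from both arms | FAS rejects |
|---|---|---|---|---|---|---|
| 5% | 20 | 1 | 3% | 5.0% | 4.9% | 5.0% |
| 10% | 40 | 4 | 13% | 7.1% | 4.9% | 5.0% |
| 20% | 40 | 8 | 25% | 13.2% | 5.0% | 5.0% |

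The simulated mean differences in PPS2 were 1.0, 4.1 and 8.0 m. Those for the FAS, and with non-takers removed from both arms, were about 0 m. Reversing the sign of D at f = 10% gave −4.0 m.

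**Would the existing PPS1 rule repair it?** SAP 6.3.4 sets expected doses equal to the duration of exposure, which ends at the last dose. A participant who takes every tablet for 21 days, stops, and returns 70 of 91 scores 21/21 = 100% and passes the 80% threshold. On placebo that person stays in PPS2; on famotidine the assay removes the same person. For early stoppers the bias is unchanged. Counted against the planned 24 weeks, the score is 21/168 = 12.5%, and the person leaves PPS2 in either arm.

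**What a 24-week denominator leaves behind.** 80% of 168 is 134.4, so 135 tablets pass. Someone who takes every tablet and stops after day 135 still passes. That person is kept on placebo and probably dropped on famotidine. The remaining bias is D times the share of such late stoppers.

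**Missing samples.** SAP 4.1 has no rule for a missing final sample. A famotidine participant without one cannot be classed as detected. A placebo participant without one might be read as not detected and kept, carrying 0 m if dead (SAP 6.4.1).

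**The case against.** The strongest reply is that little depends on PPS2. The FAS is primary for every efficacy endpoint, no decision rule uses PPS2, SAP 6.4.1.1 asks for estimates and confidence intervals, and no per protocol set is protected by randomisation. PPS2 also has a sensible aim: Protocol 6.1.1 wants to know how far the intended exposure contrast was achieved. All of this stands. It limits the point to a sensitivity analysis, and it makes the shift in metres more relevant than the rejection rate.

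The size is also uncertain. Protocol 9.4.4 expects drug discontinuation to be infrequent, so f may be small. The planned model adjusts for baseline 6MWD and functional class, so D should be read as whatever deficit remains after adjustment. The placebo arm is filtered too, by removing those who took an outside H2 antagonist, and the effect of that could go either way.

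A reader might infer from Protocol 7.1, which includes health deterioration among its reasons, that people who stop tablets are sicker. That section concerns discontinuation or withdrawal from the study. A person so withdrawn would ordinarily have no final sample. The asymmetry depends on people who stop drug but remain in follow-up, and the documents say nothing about how they fare.

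What the reply does not remove is the unequal rule itself, which is explicit in SAP 4.1 and can be changed with data the plan already collects.

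**Conclusion.** The concern holds as a conditional one. PPS2 filters the two arms on different grounds, and its estimate is biased toward famotidine by f × D if participants who stop tablets but stay in follow-up do worse regardless of drug. Over the assumed values the shift in 6MWD runs from about 1 m to 8 m, or 3% to 25% of the design effect. With D = 0 there is none, and with D negative it favours placebo.

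A reader might go further and infer that the trial's efficacy conclusion, or its type I error, is compromised. The documents do not support that: the FAS analysis does not use the assay filter and kept its 5% level in every scenario. Nor do they establish that the bias is large or certain to favour famotidine.

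That Protocol 9.3 and SAP 4.1 define the set differently, with no entry in SAP 7, is a documentation gap whatever the size of the bias.

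**What to change.** In SAP 4.1, before unblinding, redefine PPS2 as FAS participants in both arms who meet both conditions:

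- (a) By tablet count, they took at least 80% of the doses planned over the full 24 weeks. The SAP 6.3.4 denominator should not be used here. State that the count covers placebo tablets as well as famotidine.
- (b) They have a concordant final-visit assay: detected on famotidine, not detected on placebo.

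Exclude participants without a final sample from PPS2 in both arms. State that some assay-based selection remains asymmetric (late stoppers, for example) and that PPS2 is supportive only. List the departure from Protocol 9.3 in SAP 7.

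The cost is SAP wording and a somewhat smaller PPS2, since non-adherent placebo participants leave it. Tablet counts at Weeks 12 and 24 (Protocol 6.4) and the final assay are already planned.

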5.2 EXCLUSION CRITERIA

An individual who meets any of the following criteria will be excluded from participation in this study:

1. Pregnant or lactating
2. Non-group 1 pulmonary hypertension or veno-occlusive disease
3. History of interstitial lung disease, unless subject has collagen vascular disease and has pulmonary function testing conducted within 12 months demonstrating a total lung capacity or vital capacity of $\geq 60\%$
4. Has received or will receive an investigational drug, device, or study within 30 days or during the course of study
5. Left sided myocardial disease as evidenced by left ventricular ejection fraction $< 40\%$
6. Any other clinically significant illness or abnormal laboratory values (measured during the Screening period) that, in the opinion of the Investigator, might put the subject at risk of harm during the study or might adversely affect the interpretation of the study data
7. Anticipated survival less than 1 year due to concomitant disease
8. Regularly taking an H2 receptor antagonist within 30 days of enrollment
9. Creatinine clearance of < 30 mL/min
10. History of bariatric surgery
11. Current treatment for HIV

Individuals with thrombocytopenia ($< 20,000$ /microliter), coagulopathy (INR > 3), hyperkalemia (> 6), hypokalemia (< 2.5), or hyponatremia (< 125) cannot participate in the RHC sub-study. In addition, participants with known anatomic barriers to IJ placement, a latex allergy, or infection at the insertion site will be excluded from this sub-study.

Individuals with known, recent exercise associated syncope will be excluded from the cardiopulmonary exercise testing sub-study. In addition, individuals with recent myocardial infarction, unstable angina, uncontrolled arrhythmia, severe valvular stenosis, decompensated heart failure, active endocarditis, acute myocarditis or pericarditis, acute aortic dissection, or marked electrolyte abnormalities will be excluded from the CPET sub-study.

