6.5 CONCOMITANT THERAPY

For this protocol, a prescription medication is defined as a medication that can be prescribed only by a properly authorized/licensed clinician. Medications to be reported in the Case Report Form (CRF) are concomitant prescription medications, over-the-counter medications and supplements.

Participants are prohibited to take H2 receptor antagonists during the trial.

Research pharmacists will review the study participant's medications listed in their medical record and advise them about the timing of administration of their current medications with famotidine and the acid reflux concomitant medications provided. This will occur at the initial visit and as needed for any follow-up visits that have any new medications added between the visits.

According to pharmacokinetic analyses, single doses of famotidine 20mg raised intragastric pH to mean values of 5.0 (similar for when doses were given in the evening or after breakfast). There were no cumulative effects with repeated doses. However, there are many studies that have shown tachyphylaxis with repeated doses of H2RAs occurring after approximately a week of therapy. Repeated doses of H2RAs are associated with decreased time of gastric pH maintained above 4.0.

The impact on the availability of pulmonary vasodilators is as follows:

- Sildenafil: no interaction known; delayed rate of absorption with high-fat meals but not antacids (time delay 1 hr, reduced maximum concentration by 29%)
- Tadalafil: no significant interaction known; antacids reduced rates of absorption with no change in overall exposure; no significant effects observed with the co-administration of nizatidine 300mg
- Riociguat: no information available specifically with H2RAs; however, concurrent use with antacids is associated with up to 50% reduction in riociguat maximum serum concentration and 25% reduction in exposure; recommended to separate the administration of antacids and riociguat by at least 1 hr; specific mechanisms for these interactions are unknown but riociguat solubility is pH-dependent, and therefore, increases in gastric pH may be partially responsible
- Bosentan: no interaction
- Ambrisentan: no interaction
- Macitentan: no interaction
- Oral treprostinil: no interaction; bioavailability is increased by high fat, high calorie meals by up to 49% but not known to be impacted by acid suppression

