8 STUDY ASSESSMENTS AND PROCEDURES

8.1 EFFICACY AND SAFETY ASSESSMENTS

At the baseline visit participants will be consented and inclusion and exclusion criteria will be assessed for eligibility. Participants will then undergo a standardized clinical assessment with medical history, symptom assessment including NYHA functional class, vital signs (includes height, blood pressure, heart rate, oxygen saturation), weight, and physical examination. Demographics will be collected. A blood draw will include safety laboratories including comprehensive metabolic panel, complete blood count, BNP, and pregnancy test (for pre-menopausal women). The pregnancy test can be performed as either a blood or urine test. A blood-based pregnancy test is preferred; however, if a urine test is used then it must be performed by study personnel and documented in the medical record. All participants will have serum collected for mass-spectrometry at the end of the study to evaluate for contamination of the study design by individuals taking over-the-counter H2 receptor antagonists. Serum, plasma, and blood

for RNA isolation will be collected and stored for participants. Subjects will have an option to opt-out of this additional research blood sample. All participants will have a transthoracic (TTE) echocardiogram and emPHasis-10 measure of health-related quality of life. They will also complete a 6 minute walk distance (6MWD) at their baseline visit. Distance, BORG dyspnea scores, peak heart rate, oxygen saturation, and heart rate recovery at one minute will be collected to characterize the walk.

Participants who are not participating in the right heart catheterization or exercise sub-studies will be randomized and study drug will be dispensed at this visit. Participants will be instructed to take one tablet daily (20 mg of famotidine or placebo) the following day which will represent day zero and entry into the study. An antacid (Calcium Carbonate) and proton pump inhibitor (Omeprazole), both over-the-counter medications, will be provided by a study physician to participants as needed for short and long term heartburn control in an effort to try and minimize contamination of the study question by inadvertent H2 receptor antagonist use by participants attempting to self-treat heartburn with over-the-counter medications.

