6.3.4 Exposure and Compliance

Summary statistics of the duration of exposure, number of doses and the percent compliance will be presented. Percentage compliance will also be summarized by category ($\leq 60\%$, $>60\%-80\%$, $>80\%-100\%$, $>100\%-120\%$, $>120\%$, and $\geq 80\%$). The number and percentage of participants who reported taking the study drug as directed and the primary reasons for not taking the study drug as directed will be summarized by visit.

Duration of exposure (days) will be defined as Last Dose Date – Start Dose Date + 1.

Percentage compliance will be defined as Number of doses taken/ Number of doses expected *100.

Number of doses taken will be defined as the number of tablets dispensed – number of tablets returned.

Number of doses expected will be defined as duration of exposure (days)*planned daily dose.

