9 APPENDICES

9.1 Schedule of Assessments

Table 9-1: Schedule of assessments

	Baseline	Randomization	Phone Visit Week 4	Week 12	Week 24	
Visit #	1	Non-visit	PH	2	3	
Day #	-14 to -1	-1	0	28 ± 7	84 ± 7	168 ± 7
Inclusion/Exclusion Criteria	X					
Informed Consent	X					
History and physical exam						
Demographics	X					
Medical history	X					
Symptom assessment	X			X	X	
Concomitant medications	X			X	X	
Vital Signs & Weight	X			X	X	
Physical Examination	X			X	X	
Safety laboratories						
Laboratory Draw	X				X	
Comprehensive metabolic panel	X				X	
Complete blood count	X				X	
Mass-Spectrometry for H ₂ antagonists	X				X	

Pregnancy test if premenopausal	X				X
Endpoint assessment					
6 minute-walk distance (primary)	X			X	X
echocardiogram	X				X
emPHasis-10 score	X			X	X
BNP	X				X
NYHA functional class	X			X	X
Study Procedures					
Dispense study drug		X		X	
Start study drug			X		
Study drug adherence				X	X
Study drug compliance				X	X
Adverse events	X			X	X
Study Termination					X
Sub-study components					
Right heart catheterization (n=20)	X				X
Cardiopulmonary Exercise Test (n=10)	X				X
Miscellaneous					
Data Safety Monitoring Board			Semi-annually		

As per clinical practice guidelines, patients will be seen every three months with blood work and six-minute walk testing. These elements (visit, laboratory draw, comprehensive metabolic panel, complete blood count, BNP, pregnancy test, 6 minute-walk distance, and NYHA functional class) will be collected as part of routine medical care and abstracted from the medical record as research endpoints. Echocardiograms are often part of routine medical care and will be abstracted from the medical record as research endpoints; however, the frequency may be influenced by the study. To avoid any concern about overlap, any

echocardiogram occurring more frequently than annually will be considered research. It is anticipated that 1 of the 2 echocardiograms will fit this research definition. Other research elements include mass spectrometry for H2 antagonists, the emPHasis-10 score, study procedures, and sub-study components.

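### Neither per-protocol set uses the CRF record of H2 antagonist use, so a placebo participant with documented use can still count as per protocol

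*SAP*

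**What the plan says.** Protocol 6.5 states: "Participants are prohibited to take H2 receptor antagonists during the trial". The same section has over-the-counter drugs entered on the CRF. Protocol 8.1 has concomitant medication collected at every visit, and the schedules mark it at baseline, Week 12 and Week 24.

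SAP 4.1 defines two per-protocol sets, both used for sensitivity analyses of the primary and secondary efficacy endpoints:

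- **PPS1** takes FAS participants "whose famotidine medication reconciliation suggest adherence to study drug for 80% or more of administered doses". SAP 6.3.4 bases compliance on study tablets only: "Number of doses taken will be defined as the number of tablets dispensed – number of tablets returned".
- **PPS2** takes famotidine participants "for whom H₂ receptor antagonists are detected by mass spectrometry at the final visit" and "those randomized to placebo for whom H₂ receptor antagonists are not detected at the final visit".

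Protocol 9.3, SAP 4.2 (deviations are listed), SAP 6.3.1 and SAP 7 add no further condition for membership.

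On the timing of the assay the documents differ. The row "Mass-Spectrometry for H ₂ antagonists" in SAP Table 9-1 is marked at baseline and Week 24, as it is in the Protocol 1.3 schedule. Protocol 8.1 says "All participants will have serum collected for mass-spectrometry at the end of the study to evaluate for contamination of the study design", and Protocol 6.1.1 likewise describes an assay at the end of the trial.

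**The concern.** The sponsor treats contamination of the placebo arm as a real risk. Participants get a list of drugs to avoid, calcium carbonate and omeprazole are supplied, and the assay is there to measure what contamination remains. A reader of a per-protocol result will expect participants with known use of the prohibited class to have been removed. As written they are not. Tablet counts cannot register an H2 antagonist bought elsewhere, and one blood sample speaks only to dosing shortly before it was drawn.

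At stake is what PPS1 and PPS2 can be said to show. If H2 antagonists improve the endpoints, placebo participants who took them make the arms look more alike. If the rule is left open until after unblinding, any later removal of documented users becomes a post hoc choice.

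**Working it through.** **1. Who qualifies.** Take a placebo participant with at least 80% tablet compliance and CRF-recorded H2 antagonist use during treatment, and apply the SAP 4.1 rules as written.

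| Final-visit sample | PPS1 | PPS2 |
|---|---|---|
| Negative (stopped, or not dosed shortly before the draw) | in | in |
| Positive | in | out |
| None (withdrawn from the study) | in | out |

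The last row is in PPS1 because SAP 6.3.4 counts expected doses only from first to last dose. In the other arm, a famotidine participant whose positive result comes from a different H2 antagonist qualifies for PPS2, since the rule accepts any H2 antagonist.

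**2. The plan's own figures.** SAP 6.1 gives a difference of 31.9 m, SD 37.6 m and two-sided alpha 0.05. A two-sample noncentral t calculation gives power 0.963 at 40 per arm and 0.944 at 36 per arm. The SAP states 0.96 and 0.94, so its figures reproduce. This point disputes none of them.

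**3. Illustrative dilution in PPS1.** Two assumptions are not in the documents: 4 of 40 placebo participants are users, and each gains the full 31.9 m. The second is an upper bound, because it gives partial use the effect assumed for daily dosing over 24 weeks. All four can stay in PPS1:

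31.9 × 4/40 = 3.2 m (10% of the effect).

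The result scales with the assumed fraction of users. For 5%, 10%, 20% and 30% the loss is 1.6, 3.2, 6.4 and 9.6 m, which leaves 30.3, 28.7, 25.5 and 22.3 m. If users gain half the effect, each loss halves.

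**4. Illustrative dilution in PPS2.** The documents give no detection window. Assume w = 0.5 to 2 days, with use on d = 2 or 3 separated days a week continuing to the final visit.

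- Share missed = 1 − d·w/7
- Users remaining = 4 × share missed
- Placebo participants remaining = 40 − 4·d·w/7
- Dilution = 31.9 × users remaining / placebo participants remaining

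| w (days) | d (days/week) | Share missed | Users left | Placebo left | Dilution (m) |
|---|---|---|---|---|---|
| 0.5 | 2 | 0.86 | 3.43 | 39.43 | 2.8 |
| 0.5 | 3 | 0.79 | 3.14 | 39.14 | 2.6 |
| 1 | 2 | 0.71 | 2.86 | 38.86 | 2.3 |
| 1 | 3 | 0.57 | 2.29 | 38.29 | 1.9 |
| 2 | 2 | 0.43 | 1.71 | 37.71 | 1.5 |
| 2 | 3 | 0.14 | 0.57 | 36.57 | 0.5 |

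If all four stop early enough to test negative, the dilution is again 31.9 × 4/40 = 3.2 m.

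**5. Scale.** The standard error of the difference at 40 per arm is 37.6 × √(2/40) = 8.4 m, so 3.2 m is 0.38 of a standard error.

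**The case against.** The best case for the plan has four parts.

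- **Sustained recorded use should be caught.** Medication is reviewed at Week 12, deviations call for prompt corrective action, and Protocol 7.1 lets the investigator withdraw someone who cannot stay off other H2 blockers.
- **Use is visible.** SAP 6.3.3 tabulates and lists concomitant medication, deviations are listed, and Protocol 6.1.1 says that a marked departure from the expected assay pattern will be weighed when results are interpreted.
- **Single-criterion sets are legitimate.** PPS1 is an adherence set. Only PPS2 is aimed at contamination, and it uses an objective assay rather than self-report. Further exclusions after randomization can add selection bias.
- **The effect is small**, and its inputs have no source in the documents.

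The third and fourth parts stand as limits on the point: only PPS2 is directed at contamination, the sizes are illustrative, and the fix carries some selection. The first two do not answer it. Withdrawal is discretionary and defines no set, and a listing changes no one's membership.

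A reader might also infer that ignoring the baseline assay is part of the same gap. It is not, because a sample taken before dosing cannot show use during the trial. Nor do the documents support removing baseline-positive participants. The exclusion reads "Regularly taking an H2 receptor antagonist within 30 days of enrollment", so an occasional user met the entry criteria and complied with the protocol.

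**Conclusion.** The point holds on the text. Documented use of the prohibited class does not affect membership of PPS1, and affects PPS2 only if the final sample happens to show it. The resulting bias is toward no difference, provided that H2 antagonists have the hypothesised effect; with no effect there is nothing to dilute.

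Under the stated assumptions the size is at most 3.2 m in PPS1. In PPS2 it is about 0.5 to 2.8 m, rising to 3.2 m if every user stops before the draw. The number of users, their gain and the detection window are all assumed. The gap in the definitions does not depend on them.

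A reader might infer that the primary result is compromised. The documents do not support that: the primary analysis uses the FAS, which these definitions do not touch, and the power calculation is unaffected. The change is worth making because it is cheap and must be made before unblinding to be credible.

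**What to change.** **In SAP 4.1**, add one condition to both PPS1 and PPS2: no CRF-recorded, non-study H2 antagonist use between Day 0 and Week 24 beyond a stated threshold. Apply it identically in both arms and fix the threshold before unblinding. Records coded under SAP 6.3.3 can identify the drugs. The threshold should be one the CRF can support, since as-needed over-the-counter use may not come with exact day counts. Record the change in SAP 7; SAP 6.3.1 already lists reasons for exclusion from these sets.

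**Separately**, reconcile the two schedules, which mark a baseline assay, with Protocol 6.1.1 and 8.1, which describe only an end-of-study one. If the baseline sample is assayed, tabulate detection by arm at both time points. Do not use the baseline result to exclude anyone from the per-protocol sets.

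**Cost.** A few lines of SAP wording and no new data for the main change. The sets become slightly smaller and carry some further post-randomization selection, which per-protocol sets already have. The rule removes only documented use; unrecorded use still depends on the final assay. The primary analysis does not change.
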